7.2 Demographic and Baseline Characteristics of Cohorts

Demographic and baseline characteristics for each analysis set are summarized in Tables 14.1.2.1, 14.1.2.2, and 14.1.2.3 for the mITT (primary efficacy), AT (safety), and PP (secondary efficacy) analysis sets, respectively. The same table is provided for the ITT (randomized) analysis in order to evaluate baseline covariate balance achieved through randomization (Table 14.1.2.4).

Tables 14.1.3.1, 14.1.3.2, and 14.1.3.3 summarize the numbers of patients overall and by treatment group, age category, and gender, for the mITT, AT, and PP analysis sets respectively.

Prior and concomitant medication, lifetime and current medications, and surgical history will be summarized for the Safety (AT) analysis set as are all Safety endpoints. Primary and secondary efficacy endpoints are summarized for the Primary Efficacy (mITT) analysis set.

7.3 Baseline Microbiology

Table 14.1.3.4 summarizes pathogens in blood cultures and surgical samples in the ITT analysis set overall and by treatment group. Table 14.1.3.5 summarizes pathogen (genus / species) in blood culture specimens. Table 14.1.3.6 summarizes pathogen (genus / species) in intra-abdominal or debridement specimens. The data used will be based on verbatim text.

7.4 Prior and Concomitant Medication

. For all prior and concomitant medication tables, the drug class will be capitalized, and the generic drug name will be listed in small letters. The following is an example for the drug class ‘corticosteroids’.

CORTICOSTEROIDS
fluticasone
fluticasone propionate
hydrocortisone

All drug classes and all generic drug names will be reported in summary tables and in patient listings. Nephrotoxic drugs as defined in the [Appendix 7](#).

Table 14.1.4.1 will summarize the numbers (%) of patients with prior non-antimicrobial or non-nephrotoxic medications by category and by specific medication.

Table 14.1.4.2 will summarize the numbers (%) of patients with prior antimicrobial medications by category and by specific medication.

Table 14.1.4.3 will summarize the numbers (%) of patients with prior nephrotic medications by category and by specific medication.

Tables 14.1.4.4, 14.1.4.5 and 14.1.4.6 will provide the same summaries for concomitant medications.

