8.1.5 Disallowed Medications

Study participants should not receive immunosuppressant agents or chemotherapy and should not be given high doses of steroids (defined as >40 mg or 0.50 mg/kg prednisone (or steroid with equivalent activity)/day for ≥ 2 weeks (see Appendix G – Section 18.7).

NOTE: Adrenal replacement therapy (corticosteroids) is permitted in patients with septic shock at the discretion of the Investigator balancing the potential benefits and risks in this situation. The optimal treatment regimen in this setting is not resolved. Investigators are referred to current Surviving Sepsis Campaign guidelines (www.survivingsepsis.org) as a reasonable source of guidance for steroid replacement therapy in septic shock patients.

Use of agents that can cause significant nephrotoxicity (e.g. non-steroidal anti-inflammatory drugs (NSAIDS), aminoglycosides, colistin, amphotericin B) should be avoided where possible. A list of potentially nephrotoxic medications is provided in the Study Procedure Manual.

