3.4 Concomitant Medication

All concomitant medications, including ancillary, antimicrobials, immunosuppressant, and nephrotoxic drugs (with the exception of over the counter medications (unless an antimicrobial, immunosuppressant or nephrotoxic drug), vitamins, laxatives, intravenous fluid and electrolyte replacement, parenteral nutrition, topical medications (unless an antimicrobial) and other selected medications as described in the Study Procedure Manual), will be entered into the eCRF and identified by their generic or trade name. Information about antimicrobial medications immunosuppressants, and nephrotoxic drugs should include the dose, dosing frequency, route of administration, duration (start and stop times and dates), and reason for administration (to treat primary or secondary infection or for surgical prophylaxis). Information to be collected about non-antimicrobial medications should include generic or trade name, route of administration, duration (start and stop dates) and reason for administration.

Timing and adequacy of antibiotic therapy (based on institutional guidelines, baseline pathogens and antimicrobial sensitivity) will be reviewed by the Principal Investigator.

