5.12 Prior and Concomitant Medication

Medication start and stop dates will be compared to the date of first dose of study medication to allow medications to be classified as either prior or concomitant and will be recorded up to Day 29. If the start and/or stop dates of medications are missing or partially missing, the dates will be compared as far as possible with the date of administration of study drug. Medications starting after the completion/withdrawal date will be listed but will not be classified or summarized.

Medications that start and stop prior to the date of first dose of study medication will be classified as prior only.

A medication will be regarded as concomitant if it started on or after the date of first dose of study treatment.

A medication will be regarded concomitant if:

- it started prior to date of first dose of study treatment but was ongoing at the time of the first dose of study treatment.
- the start date of medication is completely unknown.

Medications are coded prior to delivery of the validated clinical data base. The following describes this process.

Drugs are coded to the WHO Drug entry that best represents (most accurately and specifically) the reported term. If a reported term is a trade name, then it will generally be coded to the trade name entry in WHO Drug that contains the correct active ingredients for that trade name. If a reported term is a generic name, then it will generally be coded to the generic entry in WHO Drug with that ingredient or combination of ingredients.

A WHO Drug entry may have one or more ATC (Anatomic-Therapeutic-Chemical) codes assigned to it within the dictionary. If a WHO Drug entry has only one ATC code, then that ATC code is additionally returned for that WHO Drug entry. If a WHO Drug entry has more than one ATC code assigned, then a single ATC code is selected based on the most common usage for the drug and the selected ATC code is additionally returned for the WHO Drug entry.

Separate sets of tables will be provided for non-antimicrobial or non-nephrotoxic medications, antimicrobial medications, and nephrotoxic medications.

6 Safety Analysis

The primary safety measures are AEs (including SAEs), deaths, clinical safety laboratory, PE, and vital signs through Day 29 including determination of survival through Day 29.

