16.1 Nephrotoxic Medications

- Acetaminophen
- Acetylsalicylic Acid
- Allopurinol
- Benazepril
- Captopril
- Celecoxib
- Enalapril
- Esmoprazole
- Famotidine
- Furosemide
- Hydrochlorothiazide
- Ibuprofen
- Iodixanol
- Iohexol
- Iopamidol
- Irbesartan
- Ketorolac
- Lansoprazole
- Lisinopril
- Losartan
- Metolazone
- Omeprazole
- Pantoprazole
- Perflutren
- Ramipril
- Ranitidine
- Sodium Amiotriazoate
- Technetium (99 M) Mebrofenin
- Valsartan
- Zesoretic

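### The SAP's nephrotoxic-medication tables leave out three of the four agents or classes the protocol names, and its date rule counts drugs finished before the infusion on the dosing day as concomitant

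*SAP*

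**What the plan says.** Protocol 8.1.5 states: "Use of agents that can cause significant nephrotoxicity (e.g. non-steroidal anti-inflammatory drugs (NSAIDS), aminoglycosides, colistin, amphotericin B) should be avoided where possible". It adds: "A list of potentially nephrotoxic medications is provided in the Study Procedure Manual". That manual is not among the documents supplied.

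The SAP does not cite the manual's list for its tables. Section 7.4 uses Appendix 7 ("Nephrotoxic drugs as defined in the"), whose section 16.1, "Nephrotoxic Medications", is a list of 30 named products beginning with "Acetaminophen". SAP section 1 says the SAP governs where it differs from the protocol.

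On layout, SAP 5.12 says: "Separate sets of tables will be provided for non-antimicrobial or non-nephrotoxic medications, antimicrobial medications, and nephrotoxic medications". Under 7.4 and Appendix 1, the nephrotoxic tables are 14.1.4.3 (prior) and 14.1.4.6 (concomitant), and the antimicrobial tables are 14.1.4.2 and 14.1.4.5. All are broken down by drug category, individual drug and treatment group in the As-Treated set.

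On timing, SAP 5.12 says: "A medication will be regarded as concomitant if it started on or after the date of first dose of study treatment". A drug begun on an earlier date but still running at the first dose is also concomitant. A drug is prior only if it both started and stopped before the dosing date. SAP 3.4 says the record for antimicrobial, immunosuppressant and nephrotoxic drugs "should include the dose, dosing frequency, route of administration, duration (start and stop times and dates"; Protocol 9.2.5 asks for the same.

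**The concern.** The primary endpoint depends on Day 28 creatinine through eGFR, and the protocol discourages nephrotoxic agents without prohibiting them. A reader of the report will want to know how many patients in each arm received such agents, and whether that was before or after the infusion. The natural place to look is the pair of tables titled as nephrotoxic medication. As defined, those tables leave out most of what the protocol itself calls significantly nephrotoxic, and the concomitant table can include exposure that was over before study drug was given. Nephrotoxin exposure is not among the subgroup variables in SAP 5.6, and the named covariates in 5.7 are drawn from that list, so no other named analysis supplies the count.

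**Working it through.** The plan states no figure here to reproduce. The check sets the passages side by side.

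**1. The list against the protocol's examples**

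| Protocol 8.1.5 | SAP Appendix 7, 16.1 | Where a course is tabulated |
|---|---|---|
| NSAIDs | Ibuprofen, ketorolac and celecoxib by name (also acetylsalicylic acid); no class entry | Named drugs: 14.1.4.3 / 14.1.4.6. Any other NSAID: 14.1.4.1 / 14.1.4.4, the non-antimicrobial or non-nephrotoxic set |
| Aminoglycosides | None | 14.1.4.2 / 14.1.4.5 only |
| Colistin | None | 14.1.4.2 / 14.1.4.5 only |
| Amphotericin B | None | 14.1.4.2 / 14.1.4.5 only |

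The last three rows follow from Protocol 8.1.6.1, which counts antibacterial and antifungal drugs as antimicrobials. Result: 0 of 30 entries cover the last three agents or classes, so 3 of 4 are absent and the fourth is partial.

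**2. Can the missing count be rebuilt from the other tables?**

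Suppose the drug rows in one arm show a, b and c patients on three of the named agents, among N treated. The number exposed to at least one lies anywhere between max(a, b, c) and min(N, a + b + c), because the rows do not say which patients overlap. The figure is therefore bounded but not given. Listing 16.2.8.44 puts antimicrobial, immunosuppressant and nephrotoxic drugs together, but as a patient listing, not a count.

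**3. The date rule against a clock rule**

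| Timing of the drug | SAP 5.12 | By clock time |
|---|---|---|
| Started and stopped before the dosing date | Prior | Prior |
| Started and stopped on the dosing date, before the infusion | Concomitant | Prior |
| Started before the infusion and still running at it | Concomitant | Concomitant |
| Started after the infusion | Concomitant | Concomitant |

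Only the second row differs. Single-dose contrast is the clearest example. CT is one of the qualifying imaging methods (Protocol 6.1), contrast for evaluating abdominal infection is allowed (8.1.6.2), and dosing falls within 6 hours of confirmed AKI (6.1).

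For scale, assume infusion times are spread evenly over the 24 hours. A drug completed h hours earlier then falls on the dosing date with probability max(0, 1 − h/24):

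- h = 2: 1 − 2/24 = 0.917
- h = 3: 1 − 3/24 = 0.875
- h = 6: 1 − 6/24 = 0.75

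These are chances for one such dose. They are not the share of patients misclassified, which depends on usage rates the documents do not give. A scan can also precede dosing by more than 6 hours, which lowers the probability.

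**4. Are clock times available?**

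SAP 3.4 and Protocol 9.2.5 call for start and stop times for antimicrobial, immunosuppressant and nephrotoxic drugs. One caveat: Protocol 8.1.6.2 has contrast recorded like other non-antimicrobial drugs, with dates only, whereas Appendix 7 lists iodixanol, iohexol and iopamidol as nephrotoxic, which brings them under the rule for times. The passages need reconciling, and whether contrast times were in fact entered should be checked.

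**The case against.** A reader might infer that the report could not reveal an imbalance between arms in nephrotoxin exposure, or that the two nephrotoxic tables are the only planned check. The documents do not support either reading. Aminoglycosides, colistin and amphotericin B each get a row by treatment group in the antimicrobial tables, where a difference in any one of them shows in full. The listed NSAIDs and contrast agents have their own rows in the nephrotoxic tables. Because the SAP plans rows by category and drug and specifies no pooled row for any nephrotoxic drug, entries such as acetaminophen do not dilute another drug's row. Table 14.1.4.3 concerns prior use only and was never a check on post-dose exposure.

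The date rule relabels exposure but drops none, applies equally to both blinded arms, and changes nothing for a course that continues across the infusion, which includes an antibiotic still being given at dosing. The protocol's agents are examples, and its fuller list is in a manual not available here, so it cannot be said whether Appendix 7 copies that list. The documents also do not show how widely the other Appendix 7 drugs are used. Finally, these tables are descriptive, and concomitant exposure is measured after randomisation, so they give context and feed no adjustment.

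All of this stands. It limits the consequence, but it does not remove the mismatch between the tables' title and their content, the missing count of exposed patients, or the mislabelled same-day drugs.

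**Conclusion.** The point holds in a limited form. The only tables labelled as nephrotoxic medication omit three of the four agents or classes Protocol 8.1.5 names and cover the fourth in part, so they understate exposure as the protocol describes it. No planned table gives the number of patients exposed to any of those agents. The concomitant table also takes in drugs completed before the infusion on the dosing date.

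A reader might go further and take this as a threat to the primary result. It is not: that comparison is an unadjusted chi-square test (SAP 5.2) that uses none of these tables, so no estimate, error rate or decision changes. What is affected is the accuracy of two descriptive counts and how they are read.

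The omission is a matter of reading the list and rests on no assumption. The size of the date effect rests on the even spread of dosing times assumed above, and the number of patients affected is unknown.

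**What to change.** Before unblinding:

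1. Reconcile Appendix 7 section 16.1 with Protocol 8.1.5 and the Study Procedure Manual list, and define entries by class so that unlisted members are captured.
2. Cross-flag nephrotoxic antimicrobials so that they count in the nephrotoxic tables as well as the antimicrobial tables.
3. In 5.12, classify antimicrobial, immunosuppressant and nephrotoxic drugs as prior or concomitant by recorded date and time relative to the infusion. Where only a date exists, show dosing-day use with unknown time separately.
4. Add one row per arm: patients with any protocol-named nephrotoxin started after dosing, through Day 28. Restrict it to those agents, since widely used entries in the longer list could otherwise mask a difference.

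The cost is an appendix edit and a small amount of recoding. Drug names are already collected, as are times for these classes, subject to the check on contrast. The primary analysis and the visit schedule stay as they are.

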7.5 Medical and Surgical History

Table 14.1.5.1 will summarize the numbers and percentages of patients that experienced medical conditions during their lifetime by body system and specific medical conditions when experienced by more than one patient in either group.

Table 14.1.5.2 will summarize the numbers and percentages of patients with current medical conditions by body system and specific medical conditions when experienced by more than one patient in either group.

Table 14.1.6.1 will summarize the numbers and percentages of patients that underwent specific surgical procedures at any time during their lifetime summarized body system and specific surgical procedures.

Table 14.1.6.2 will summarize the numbers and percentages of patients with specific types of surgical or interventional procedures to establish source control and location of source control.

Table 14.1.6.3 will summarize the numbers and percentages of patients according to acuity of AKI,, whether or not a reference pre-infection creatinine value was used, and whether the diagnosis of AKI was based on creatinine alone, urine outcome alone, or both..

7.6 Drug Administration and Timing

Drug administration and timing will be performed for two sets of subjects separately.

- Patients presenting with abdominal sepsis or NSTI and AKI are to have drug administered within 6 hours of decision to go to abdominal surgery or interventional radiology procedure, or surgical confirmation of NSTI.
- Patients who present just with abdominal infection or NSTI and then followed for development of AKI are to have drug administered within 6 hours of diagnosis of AKI

Time to drug allocation, drug administration time point (during, or after surgery), and the actual volume of drug infused will be described in Table 14.1.7.1.

7.7 Patient Disposition and End of Study Status

Table 14.1.8.1 summarizes Day 29 study status by treatment group.

8 Presentation of Efficacy Results

8.1 Primary AKI Endpoint

The numbers and percentages of patients in each group meeting the primary efficacy endpoint of complete recovery (*freedom from durable loss of renal function at Day 28*) is summarized in Table 14.2.1.1 for the mITT (primary efficacy) analysis set. This table also includes the statistical significance of this endpoint based on an unadjusted chi-square statistic. Study success requires one-sided $p \leq 0.05$ for this endpoint which is equivalent to a two-sided $p \leq 0.10$ as long as the percentage of subjects achieving the endpoint is larger in the actively treated group compared to placebo. This table also provides the estimated treatment group difference and 90% confidence interval corresponding to the one-sided significance level. The lower bound of the 90% confidence interval is equivalent to the lower bound of a 1-sided 95% confidence interval. Based on the study data, it can be concluded that the true difference in success rates is at least equal to the lower bound of the 1-sided 95% confidence intervals. Table 14.2.1.1 also provide the same summaries for the components of the primary endpoint.

- Alive at Day 28,
- Free of dialysis at Day 28, and
- Less than a 37% loss of estimated Glomerular Filtration Rate (eGFR; measured with the Modification of Diet in Renal Disease (MDRD) formula from the patient's reference eGFR) at Day 28.

Table 14.2.1.2, and 14.2.1.3 repeat these analyses in the AT and PP analysis sets, respectively.

8.2 Evaluation of Site Heterogeneity in Primary Endpoint Treatment Effects

Table 14.2.1.4 provides comparisons of the percentages of patients achieving the primary efficacy endpoint by site, overall and by treatment group in the mITT analysis. If needed, site-to-site heterogeneity will be evaluated with these data using a random effects meta-analysis approach as described above.

8.3 Secondary and Exploratory AKI Recovery Endpoints

Table 14.2.2.1 summarizes treatment group comparisons based on secondary AKI recovery endpoints in the mITT analysis set including:

- Freedom from durable loss of renal function at Day 14
- Freedom from durable loss of renal function at Day 90
- Improvement or freedom from durable loss at Day 14
- Improvement or freedom from durable loss at Day 28
- Improvement or freedom from durable loss at Day 90

Tables 14.2.2.2 and 14.2.2.3 repeat these comparisons in the AT and PP analysis sets, respectively.

8.4 mSOFA Scores

Table 14.2.4.1 summarizes observed modified total score, organ specific scores, and mSOFA total scores at Screening, Day 1, Day 3, Day 7, and Day 14.

Table 14.2.4.2 provides the same summary after application of last-value-carried forward (LOCF). LOCF was not applied after patient death.

Table 14.2.4.3 summarizes mSOFA at Screening and changes from Screening to Day 1, Day 7, and Day 14 for observed cases.

Table 14.2.4.4 provides the same summary after application of LOCF.

Table 14.2.4.5 summarizes the percentages of subjects with resolution of organ dysfunction (organ resolution is defined as having a total mSOFA score of ≤ 1) at day 14 and the resolution of specific organ dysfunction defined as having an individual organ SOFA score of ≤ 1 at Day 14.

8.5 Critical Care and Hospital Stay Parameters, to be Measured until Day 28

The following critical care and hospital stay parameters will be assessed.

- Hospital length of stay (days)
- ICU free days
- Days in ICU
- Days on ventilator
- Ventilator free days
- Vasopressors days
- Vasopressors free days
- Discharge status

Because of the expected skewness in the distributions of these parameters, non-parametric Wilcoxon rank sum tests will be used to assess the nominal statistical significance of treatment group differences in these parameters. Table 14.2.5.1 will provide summary statistics by treatment groups including N, mean, median, standard deviation, and minimum, and maximum values.

Table 14.2.5.2 summarizes hospital discharge status.

Table 14.2.5.3 summarizes hospital readmissions.

Table 14.2.5.4 will summarize critical care and hospital stay parameters over days 1 to 28 comparing by primary effectiveness status (success versus failure).

Table 14.2.5.5 will summarize critical care and hospital stay parameters over days 1 to 28 comparing subjects with Day 14 mSOFA ≤ 1 versus Day 14 mSOFA ≥ 2 .

Table 14.2.5.6 provides the same information as in Table 14.2.5.6 but for the PP analysis set.

Tables 14.2.5.7 and 14.2.5.8 provide the same information as Tables 14.2.5.1 and 14.2.5.6 but restricted to subjects alive at Day 14.

8.6 Time-to-Event and Survival Analyses

Tables 14.2.6.1 and 14.2.6.2 provide life table analyses for mortality to Day 90 in the Reltecimod and Placebo groups, respectively in the mITT analysis set. Tables 14.2.6.6 and 14.2.6.7 repeat these analyses in the PP analysis set. Tables 14.2.6.3, 14.2.6.4, and 14.2.6.5 provide life table analyses for mortality to Day 90 for subjects randomized to Reltecimod, Placebo, and for both groups, respectively, among subjects achieving Freedom from Durable Loss of Renal Function at Day 28. Kaplan-Meier survival curves will be provided for each of these analyses with cumulative mortality plotted on the y-axis.

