- Upon study drug administration patient is transitioned to Visit 2 (Day 1)

Visit 2 (Day 1)

Starts only upon study drug administration and terminates at the end of the calendar day. For abdominal sepsis, study drug may be given prior to, during, or after surgery if meets

all criteria. For NSTI, study drug may only be given during surgery or immediately after surgery (after surgical confirmation of NSTI).

- Drug (to be infused over 10 minutes) should be administered within 6 hours, under the following criteria, whichever is later, (as described in inclusion criteria Section 6.1):

- After confirmation of Stage 2 or 3 AKI as established at the study site

AND

A. Abdominal Infection

- After the decision is made by the attending surgeon at the study site for a surgical or interventional radiology procedure for the abdominal infection

OR

- After confirmed diagnosis of abdominal infection has been established by a surgical or interventional radiology procedure

OR

B. Necrotizing Soft Tissue Infection

- After surgical confirmation of NSTI (drug should not be administered until surgical confirmation of NSTI is established)

Note: If a surgical or interventional radiology procedure for the abdominal infection, or surgical confirmation of NSTI, occurred at an outside hospital prior to transfer to the study site, study medication must be administered within 6 hours of re-established diagnosis of Stage 2 or 3 AKI at the study site.

- Record if overdose
- Record any follow-up surgical or interventional radiologic procedures for previously documented abdominal infection or NSTI
- Collection of AEs/ SAEs
- Concomitant medications
- Vital signs (first set of vitals on that day)
- Symptom-driven interim PE
- Fluid balance (total in/out-I/O) for calendar day starting from the time accurate I/Os recorded (start time may be prior to study drug administration)
- Detailed urine output
 - Should be recorded continuously from time of study drug administration to Day 7 (if still in ICU or step down unit), using most frequent hourly intervals available and by calendar day with or without Foley catheter in place
- Spot urine for albumin to creatinine ratio
- Collect data on acute RRT
- Record additional relevant procedures related to the kidney (e.g., renal biopsy)
- Record any imaging that evaluates the kidney
- Weight, only if not collected at screening
- Collect data on additional amputations if NSTI

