4.1 Primary Effectiveness Endpoint

The primary effectiveness endpoint is *freedom from durable loss of renal function at Day 28*. The primary effectiveness endpoint requires:

- (i) Alive at Day 28,
- (ii) Free of dialysis at Day 28, and
- (iii) Less than a 37% loss of estimated Glomerular Filtration Rate (eGFR; measured with the Modification of Diet in Renal Disease (MDRD) formula from the patient's reference eGFR) at Day 28.

Reference creatinine values, baseline AKI stage and percentage loss of eGFR at 28 will be determined through algorithmic determination (see details above). Percentage loss of eGFR determined algorithmically will be based on a comparison of eGFR at screening compared to an algorithmically determined reference creatinine value.

Note: The Clinical Protocol allows subjects to qualify for enrollment in terms of AKI stage through urine outcome.

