4.2 Secondary Effectiveness Endpoints

The secondary effectiveness endpoints for this study are:

- Freedom from durable loss of renal function at Day 14
- Freedom from durable loss of renal function at Day 90

Reference creatinine values, baseline AKI stage and percentage loss of eGFR at Days 14 and 90 will be determined through algorithmic determination (see details above). Percentage loss of eGFR determined algorithmically will be based on a comparison of eGFR at screening compared to an algorithmically determined reference creatinine value

- Resolution of organ dysfunction (organ resolution is defined as having a total mSOFA score of ≤ 1) at Day 14
- Resolution of specific organ dysfunction (defined as having an individual organ mSOFA score of ≤ 1) at Day 14
- Critical care and hospital stay parameters
 - Hospital length of stay
 - ICU length of stay
 - ICU-free days in 28 days
 - Days on ventilator
 - Ventilator free days in 28 days
 - Vasopressor days
 - Vasopressor free days in 28 days
 - Discharge status

- Patient survival at Days 14, 28 and 90.
- Presentation of Stages 1, 2, or 3 AKI (using the KDIGO criteria)
- **Stratifications involving Day 14 mSOFA \leq 1 vs Day 14 mSOFA \geq 2**
 - Compare critical care between Day 14 mSOFA \leq 1 vs Day 14 mSOFA \geq 2
 - Compare dose groups in those with Day 14 mSOFA \leq 1
 - Compare dose groups in those with Day 14 mSOFA \geq 2
- Among patients presenting with cardiovascular failure (shock), dose group predicting Day 14 mSOFA \leq 1
- Survival to Day 90 as a function of *freedom from durable loss of renal function at 28* (overall and by dose group)

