5.10 Analysis of Event-time and Overall Survival

Time-to-event endpoints will be assessed in descriptive analyses using survival and life table methods as appropriate and illustrated using Kaplan-Meier survival curves⁷. The significance of group will be assessed using logrank statistics.

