49	14.2.5.5	Critical Care and Hospital Stay Parameters Over Days 1 to 28 Comparing Subjects with Day 14 mSOFA \leq 1 to Day 14 mSOFA \geq 2 mITT Analysis Set
50	14.2.5.6	Critical Care and Hospital Stay Parameters Over Days 1 to 28 By Treatment Group PP Analysis Set†
51	14.2.5.7	Critical Care and Hospital Stay Parameters Over Days 1 to 28 By Treatment Group mITT Analysis Set† Alive at Day 14
52	14.2.5.8	Critical Care and Hospital Stay Parameters Over Days 1 to 28 By Treatment Group PP Analysis Set Alive at Day 14†

Survival and Time-to-Event Analyses		
53	14.2.6.1	Life Table Analysis to Day 90 Mortality – Reltecimod 0.5 mg/kg mITT Analysis Set
54	14.2.6.2	Life Table Analysis to Day 90 Mortality – Placebo mITT Analysis Set
55	14.2.6.3	Life Table Analysis to Day 90 Mortality – Subjects with Freedom from Durable Loss of Renal Function at Day 28 mITT Analysis Set – Reltecimod 0.5 mg/kg
56	14.2.6.4	Life Table Analysis to Day 90 Mortality – Subjects with Freedom from Durable Loss of Renal Function at Day 28 mITT Analysis Set – Placebo
57	14.2.6.5	Life Table Analysis to Day 90 Mortality – Subjects with Freedom from Durable Loss of Renal Function at Day 28 mITT Analysis Set – All
58	14.2.6.6	Life Table Analysis to Day 90 Mortality – Reltecimod 0.5 mg/kg PP Analysis Set
59	14.2.6.7	Life Table Analysis to Day 90 Mortality – Placebo PP Analysis Set
60	14.2.6.8	Life Table Analysis to Day 90 Mortality – Reltecimod 0.5 mg/kg mITT Analysis Set in Subjects Presenting with Shock
61	14.2.6.8	Life Table Analysis to Day 90 Mortality - Placebo mITT Analysis Set in Subjects Presenting with Shock
62	14.2.6.8	Life Table Analysis to Day 90 Mortality – Day 14 mSOFA ≤ 1 mITT Analysis Set
63	14.2.6.8	Life Table Analysis to Day 90 Mortality – Day 14 mSOFA ≥ 2 mITT Analysis Set
		C-Reactive Protein
64	4.2.7.1	C-Reactive Protein at Screening and at Days 7, 14, and 29 and Changes from Screening by Treatment Group mITT Analysis Set†

		Adverse Events
65	14.3.1.1	Summary of Treatment-Emergent Adverse Events (TEAEs) By Treatment Group As Treated (Safety) Analysis Set†
66	14.3.1.2	Incidence Rates (%) and Event Counts of TEAEs by System Organ Class and Preferred Term By Treatment Group As Treated (Safety) Analysis Set†
67	14.3.1.3	Incidence Rates (%) and Event Counts of TEAEs Sorted by Descending Incidence of Preferred Term As Treated (Safety) Analysis Set†

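### The Day 90 survival endpoint conditioned on Day 28 success has no survivor comparator, and Table 14.2.5.4 mixes early deaths into the failure group, so part of any association is built in

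*SAP*

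**What the plan says.** SAP 4.1 makes "Alive at Day 28" the first condition of the primary endpoint, so every death before Day 28 is a failure.

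SAP 4.2 then lists among the secondary effectiveness endpoints "Survival to Day 90 as a function of" that same Day 28 status, overall and by dose group.

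SAP 8.6 implements this with Tables 14.2.6.3 (Reltecimod), 14.2.6.4 (placebo) and 14.2.6.5 (both), which are life tables "among subjects achieving Freedom from Durable Loss of Renal Function at Day 28". SAP Appendix 1 lists the same three, for "Subjects with Freedom from Durable Loss of Renal Function at Day 28", and none for Day 28 failures. The whole-cohort Tables 14.2.6.1 and 14.2.6.2 are described in the same terms: they "provide life table analyses for mortality to Day 90" in each arm. Neither SAP 8.6 nor SAP 5.10 gives a time origin or a landmark. In Protocol 7.3, the Day 1 visit "Starts only upon study drug administration and terminates at the end of the calendar day".

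SAP 8.5 adds Table 14.2.5.4, critical care and hospital stay over Days 1 to 28, "comparing by primary effectiveness status (success versus failure". It has no survivor restriction, although Tables 14.2.5.7 and 14.2.5.8 in the same section are limited to patients alive at Day 14. Under SAP 4.4, days on which a patient is not alive earn no free days.

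**The concern.** The success group cannot contain a death before Day 28. Any survival figure covering Days 1 to 28 therefore favours successes by construction over a group that includes early deaths. The SAP names the relation between success and Day 90 survival as an endpoint, but the only comparators it tabulates are the whole-cohort tables, which do include those deaths.

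A reader who sets Table 14.2.6.3 beside 14.2.6.1, or 14.2.6.4 beside 14.2.6.2, could take the difference as evidence that renal success at Day 28 predicts later survival. Some of that difference would appear even if renal status had no bearing on death after Day 28.

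Table 14.2.5.4 has a related problem that needs no inference about the clock. It contrasts success with failure directly, and the failure group holds all the early deaths.

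**Working it through.** **The plan's own figure.** The SAP states no number for the Day 90 analysis, so there is nothing to reproduce for it.

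**Inputs**
- *m*, mortality by Day 28: assumed, 9.3% to 30%. The low end is the Phase 2 study in Protocol 4.1.3.3.2, 4 deaths among 43 patients (4/43 = 9.3%). Those were NSTI patients and not all had AKI. The upper values are assumptions only.
- *q*, mortality from Day 28 to Day 90: assumed 10% (5% as a check), and equal in all Day 28 survivors. Equality is the no-association condition.
- *S*, overall success rate: (75% + 50%)/2 = 62.5%, from the rates in SAP 2.1.2. It is used only in steps 3 and 4.

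**Step 1: success-only tables against whole-cohort tables**
- Day 90 survival, successes: 1 − q.
- Day 90 survival, whole cohort: (1 − m)(1 − q).
- Gap: (1 − q) − (1 − m)(1 − q) = m(1 − q). It does not depend on *S*.

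| m | Successes | Whole cohort | Gap, q = 10% | Gap, q = 5% |
|---|---|---|---|---|
| 9.3% | 90.0% | 0.907 × 0.90 = 81.6% | 8.4 points | 0.093 × 0.95 = 8.8 points |
| 20% | 90.0% | 0.80 × 0.90 = 72.0% | 18.0 points | 0.20 × 0.95 = 19.0 points |
| 30% | 90.0% | 0.70 × 0.90 = 63.0% | 27.0 points | 0.30 × 0.95 = 28.5 points |

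The whole-cohort tables are by arm, so the formula applies within an arm with that arm's own *m*.

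**Step 2: Day 28 landmark**
- Failures alive at Day 28 have Day 90 survival 1 − q = 90%. Successes also have 90%. The gap is zero, as it should be under the assumption.
- The success estimate does not change when the clock moves from Day 1 to Day 28, because no success can die in between. The correction comes from the comparator.

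**Step 3: Table 14.2.5.4**
- Share of failures who died by Day 28: m/(1 − S).
- m = 9.3%: 9.3/37.5 = 24.8%. m = 20%: 20/37.5 = 53.3%. m = 30%: 30/37.5 = 80%.
- Among successes the share is zero.
- A patient who dies on Day 8 forfeits the 28 − 8 = 20 later days on every free-day measure, whatever the earlier course. Free days among failures are pulled down by definition.
- Plain durations (hospital stay, ICU, ventilator and vasopressor days) stop at death, so early death can pull these the other way. The table therefore mixes two distortions of opposite direction.

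**Step 4: size of the landmark comparator**
- Failures alive at Day 28 out of 120: 120 × (0.375 − m).
- m = 9.3%: 120 × 0.282 ≈ 34. m = 20%: 120 × 0.175 = 21. m = 30%: 120 × 0.075 = 9.
- Expected deaths by Day 90 at q = 10%: about 3.4, 2.1 and 0.9.

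**The case against.** The strongest reply is that the SAP never plans a survival comparison of successes with failures. That is correct. Tables 14.2.6.3 to 14.2.6.5 cover successes only. SAP 5.10 says "The significance of group will be assessed using logrank statistics" but does not name success status as the group. A reader might infer a planned success-versus-failure contrast starting at Day 1. With S = 62.5%, m = 20% and q = 10%, that would show 90% against (17.5/37.5) × 0.90 = 42%. In 2,000 simulated trials of 120 patients, with 10% later mortality in everyone, a two-sided 5% log-rank test on that contrast rejected in 90% to 100% of trials across m = 9.3% to 30%, against 3.6% to 4.7% with a Day 28 landmark. Those figures describe an analysis found in no listed table, so the point does not rest on them. A Day 1 origin is also the natural reading rather than a stated rule.

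The arm comparison within successes (14.2.6.3 against 14.2.6.4) has no differential guaranteed survival, since both arms carry the same 28 days. Its weakness is that it conditions on a post-randomization outcome.

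A reader might also extend the point to the Day 90 life tables by Day 14 mSOFA. The SAP does not support that. Sections 5.4 and 5.11.3 bar carrying scores forward after death, so patients who die before Day 14 may enter neither group. Section 5.11.3 also wants a Day 14 value for every patient, but this is at most an ambiguity.

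Finally, the analyses are descriptive. That limits the consequence. It does not supply the comparator that the endpoint in SAP 4.2 needs, and Table 14.2.5.4 does compare success with failure as written.

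**Conclusion.** The point holds in a limited form and should be addressed. The endpoint in SAP 4.2 calls for a comparison, and the only survival tables available for it include all deaths before Day 28, which successes cannot have. Under the stated assumptions this alone produces a gap of 8 to 27 points at Day 90 (up to 28.5 at 5% later mortality), with no true association after Day 28. These sizes rest on assumed mortality; only the 9.3% has an anchor in the documents, and it comes from a different population.

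It would be too strong to say that the definition creates the whole association. A real relation after Day 28 may exist as well, and the documents do not allow its size to be judged. Part of any observed association is built in, and the tables as planned cannot separate that part from the rest.

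In Table 14.2.5.4 the free-day measures are biased against failures by definition, while the direction for plain durations is uncertain. The primary test is unaffected.

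**What to change.** Before the SAP is finalized ahead of unblinding:

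1. For the SAP 4.2 endpoint, specify a Day 28 landmark: patients alive at Day 28, with time counted from Day 28 to Day 90. State this origin in SAP 8.6.
2. Add a life table for failures alive at Day 28 as the comparator for Tables 14.2.6.3 to 14.2.6.5, overall and by arm.
3. Label the result descriptive and non-causal, including the arm comparison within successes.
4. Restrict Table 14.2.5.4 to Day 28 survivors, or add that version beside the planned one.

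The cost is SAP wording and table programming; no new data are needed. The downside is size: step 4 of the working gives roughly 9 to 34 surviving failures in a trial of 120, with few later deaths. The landmark comparison will be imprecise and should be presented with its numbers at risk.
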